**CONFIDENTIAL**

207660

The number and percentages of participants who experience at least one AE will be presented for AEs below. This summary will include only AEs that occurred within 84 days in Blind Phase.

- Common AEs ( $\geq 3\%$ ) within 84 days in Blind Phase by Sex (by overall frequency)
- Common AEs ( $\geq 3\%$ ) within 84 days in Blind Phase by Age group (Age  $< 65$ , Age  $\geq 65$ ) (by overall frequency)

“Common ( $\geq 3\%$ ) AEs” is defined as the percentage of AEs is more than and equal to 3% in either treatment group.

In addition, the items below will be listed.

- All AEs
- Participant Numbers for Individual AEs
- Fatal Serious AEs
- Non-Fatal Serious AEs
- Reasons for Considering as a Serious AE
- AEs Leading to Withdrawal from Study
- Relationship between AE SOC, PT and Verbatim Text.

## **8.2. Adverse Events of Special Interest Analyses**

Adverse Events of Special Interest are defined as below.

- Convulsions and Seizures
- Respiratory Adverse Events
- Possible Distant Spread of Toxin

The number and percentage of AESI will be presented by treatment cycle and treatment group. The details of how to identify are described in the [Appendix 13](#).

## **8.3. Clinical Laboratory Analyses**

Laboratory evaluations including the analyses of Chemistry laboratory tests, Hematology laboratory tests, Urinalysis, and liver function tests will be based on GSK Core Data Standards. The details of the planned displays are in [Appendix 12](#): List of Data Displays.

These data at Screening Visit, in Blind Phase and at Final Visit will be summarized by visit. Data at all visits for participants with any value outside normal range will be listed.

Values and change from baseline in Chemistry Laboratory tests and Hematology laboratory tests will be summarized by treatment group and visit.

Worst case results relative to normal range from baseline will be presented for Chemistry, Hematology and Urinalysis. Worst case urinalysis results relative to baseline for protein (category: NEG, TRA, 1+, 2+, 3+, 4+) and occult blood (category: NEG, TRA, 1+, 2+, 3+) urinalysis only will be summarized by treatment group. The categories for worst case

CONFIDENTIAL

207660

are: No Change/Decreased, Any Increase, Increase to TRA, Increase to 1+, Increase to 2+, Increase to 3+, Increase to 4+. The categorization is determined by comparing the baseline category to the worst case post-baseline category. The determination of the worst case post-baseline takes into account both planned and unscheduled assessments. The percentages are based on the number of subjects in the treatment group with data for the test post-baseline. Subjects with missing baseline value are to be assumed to have normal/within range baseline value.

Shifts from baseline relative to normal range will be summarized by treatment group and visit for Chemistry and Hematology values.

Scatter plot of Chemistry and Hematology at Week 12 versus baseline in Blind Phase will be presented.

The outputs regarding liver events will not be presented unless at least one liver event is observed. See the details in the [Appendix 12](#).

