## CONFIDENTIAL

207660

Overview of Study Design and Key Features	
	
muscles that act on the finger (including thumb flexors) and wrist flexors, and 160 units into the muscles that act on the elbow flexors. A total of 400 units of the product will be injected.
 
 
• In the 240-unit group, 240 units of the product will be injected into the muscles that act on the finger (including thumb flexors) and wrist flexors. Placebo will be injected into the muscles that act on the elbow flexors. A total of 240 units of the product will be injected.
 
• In the Open-label phase, a total of 400 units will be injected in both groups. 
 
• The product can be injected up to 3 times after completion of Part 1 in the blind phase. Participants whom the investigator considers as eligible for the injections will be treated. The next injections cannot be performed until the eligibility of the participant has been confirmed by the investigator.
 
• The muscle to be injected and the dose will be decided by the investigator based on the patient's symptoms, and a total dose of 400 units of the product will be injected in a divided dose. For the muscles that the investigator considers as unnecessary to be treated, an injection may be skipped. The involving muscle and the dose do not have to be same each time always.
 
 
 

Treatment Assignment	
 
• Number of participants (randomized participants): 120 (60 per group)
 
• GSK RandAll NG will be used to generate the randomization schedule.
 
• The randomization will be stratified by the MAS score (3 or 4) in the elbow flexors at Day1
 

Interim Analysis	
 
• Interim analysis is planned in this study as described in 3.1.
 

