**CONFIDENTIAL**

207660

The participant is re-treated at Week 20 visit in Blind Phase and completes the Week 4 visit in Open-label Phase.

The participant completes the Week 24 visit in Blind Phase.

2. All required database cleaning activities have been completed and interim database release and database freeze has been declared by Data Management.
3. All criteria for unblinding the randomization codes have been met.
4. Randomization codes have been distributed according to RandAll NG procedures.
5. Interim analyses will be performed.

The interim analyses will be performed for regulatory submission. However subject level data will not be disclosed to people who work at the sites including investigators.

All planned interim analyses (i.e. Study population, Efficacy and Safety analyses) will be performed using data up to Week 24 visit for all participants.

For Rehabilitations, the data at Screening visit and Week 12 visit will be used for the interim analysis.

For Adverse Events, Liver Events and Medication, the data up to Week 24 visit is defined by using the start date. If the start date of these data is earlier than or same as the date of Week 24 visit defined above, these data will be included in the data up to Week 24 visit. Otherwise the data will not. See the decision tree ([Appendix 14](#)) to determine the Week 24 visit and date of the participant.

Cardiovascular Events will not be output in the interim analysis.

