Physical examination (simplified version)		X 				X		X 1,t				X		X
Medical history	X	X 												
Vital signs m	X	X 				X		X 1,t				X		X
Height	X													
Body weight	X					X u	X u					X u	X u	
Pulmonary function test	X	X				X	X u					X	X u	X
Electrocardiogram	X					X u	X u					X u	X u	
Pregnancy test n	X	X 				X u	X u					X s, u	X u	X
Laboratory test o	X					X						X		X
Adverse events p	X	X	X	X	X	X	X	X	X	X	X	X	X	X
Concomitant medications/therapies	X	X 	X	X	X	X	X	X	X	X	X	X	X	X
Testing for neutralising antibodies q	X					X								X

- Test items for screening must be performed from 4 weeks to 1 weeks before Day 1 visit (±3 days).
- Eligibility evaluation (Qualification for Retreatment Visit: QRV) will be performed at V5 as a starting point if a participant does not meet the criteria only. The evaluation is performed at a 4-week interval, V5 as a starting point, The QRV when a participant meets the criteria will be a same day as the injection in the next treatment period.
- If a participant is evaluated to meet the eligibility for the injection in the blind phase at V5, the participant will move forward to Part 2 in the open-label phase (Namely, V5 in Part 1 and V1 in Part 2 is a same day). If the participant does not meet the eligibility, QRV will be performed 4 weeks later, at V5 as a starting point.
- If a participant is evaluated to meet the eligibility at V5 in the open-label phase, the participant will move forward to the next treatment phase (V5 and V1 in the next treatment phase is a same day). If the participant does not meet the eligibility, QRV is performed 4 weeks later, V5 as a starting point. If V5 in each treatment phase is at Week 48 after initial injection, V5 will be considered to be completion visit (FV). However, for the testing items, pre-scheduled tests at

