3.37.	Safety 1	AE1	Summary of Adverse Events until Week 24 visit Leading to Withdrawal from Study by System Organ Class and Preferred Term	IDSL Treatment Emergent AE See the Section 10.4.2 Three treatment arms (240, 400 and 240 + 400U)	IA SAC

CONFIDENTIAL

207660

Safety: Tables					
No.	Population	IDSL / Example Shell	Title	Programming Notes	Deliverable
3.38.	Safety 1	AE1	Summary of Adverse Events until Week 24 visit Leading to Withdrawal from Study by System Organ Class and Preferred Term in Blind Phase	Blind Phase (until second dose) See the Section 10.4.2. Two treatment arm (240 and 400U)	IA SAC
3.39.	Safety 1	AE1	Summary of Adverse Events Leading to Withdrawal from Study within 84 days from the initial dose by System Organ Class and Preferred Term	Blind Phase (within 84 days) See the Section 10.4.2. Two treatment arm (240 and 400U)	IA SAC
3.40.	Safety 2	AE1	Summary of Adverse Events until Week 24 visit Leading to Withdrawal from Study by System Organ Class and Preferred Term in Open Label Phase (2nd Treatment)	Open Label Phase (2nd Treatment) See the Section 10.4.2. Three treatment arms (240, 400 and 240 + 400U)	IA SAC
Laboratory: Chemistry					
3.41.	Safety 1	LB1	Summary of Chemistry by Visit	Summarize data at Screening Visit and in Blind Phase.	IA SAC
3.42.	Safety 1	LB1	Summary of Chemistry Changes from Baseline by Visit	Summarize data in Blind Phase. ICH E3	IA SAC
3.43.	Safety 1	LB3	Summary of Chemistry Shifts from Baseline Relative to Normal Range		IA SAC
3.44.	Safety 1	LB15	Summary of Worst Case Chemistry Results Relative to Normal Range Post-Baseline Relative to Baseline	ICH E3	IA SAC
Laboratory: Hematology					
3.45.	Safety 1	LB1	Summary of Haematology by Visit	Summarize data at Screening Visit and in Blind Phase.	IA SAC
3.46.	Safety 1	LB1	Summary of Hematology Changes from Baseline	Summarize data in Blind Phase. ICH E3	IA SAC

CONFIDENTIAL

207660

Safety: Tables					
No.	Population	IDSL / Example Shell	Title	Programming Notes	Deliverable
3.47.	Safety 1	LB3	Summary of Hematology Shifts from Baseline Relative to Normal Range		IA SAC
3.48.	Safety 1	LB15	Summary of Worst Case Hematology Results Relative to Normal Range Post-Baseline Relative to Baseline	ICH E3	IA SAC
Laboratory: Urinalysis					
3.49.	Safety 1	UR1	Summary of Worst Case Urinalysis Results (Discrete or Character Values) Post-Baseline Relative to Baseline	ICH E3	IA SAC
Laboratory: Hepatobiliary (Liver)					

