3.116.	Safety 2	AE1	Summary of Adverse Events Leading to Withdrawal from Study by System Organ Class and Preferred Term in Open Label Phase (2nd Treatment)	Open Label Phase (2nd Treatment) See the Section 10.4.2 . Three treatment arms (240, 400 and 240 + 400U)	SAC
3.117.	Safety 3	AE1	Summary of Adverse Events Leading to Withdrawal from Study by System Organ Class and Preferred Term in Open Label Phase (3rd Treatment)	Open Label Phase (3rd Treatment) See the Section 10.4.2 . Three treatment arms (240, 400 and 240 + 400U)	SAC

CONFIDENTIAL

207660

Safety: Tables					
No.	Population	IDSL / Example Shell	Title	Programming Notes	Deliverable
3.118.	Safety 4	AE1	Summary of Adverse Events Leading to Withdrawal from Study by System Organ Class and Preferred Term in Open Label Phase (4th Treatment)	Open Label Phase (4th Treatment) See the Section 10.4.2. Three treatment arms (240, 400 and 240 + 400U)	SAC
Laboratory: Chemistry					
3.119.	Safety 1	LB1	Summary of Chemistry by Visit	Summarize data at Screening Visit, in Blind Phase and at Final Visit.	SAC
3.120.	Safety 1	LB1	Summary of Chemistry Changes from Baseline by Visit	Summarize data in Blind Phase and at Final Visit. ICH E3	SAC
3.121.	Safety 1	LB3	Summary of Chemistry Shifts from Baseline Relative to Normal Range		SAC
3.122.	Safety 1	LB15	Summary of Worst Case Chemistry Results Relative to Normal Range Post-Baseline Relative to Baseline	ICH E3	SAC
Laboratory: Hematology					
3.123.	Safety 1	LB1	Summary of Hematology by Visit	Summarize data at Screening Visit, in Blind Phase and at Final Visit.	SAC
3.124.	Safety 1	LB1	Summary of Hematology Changes from Baseline	Summarize data in Blind Phase and at Final Visit. ICH E3	SAC
3.125.	Safety 1	LB3	Summary of Hematology Shifts from Baseline Relative to Normal Range		SAC
3.126.	Safety 1	LB15	Summary of Worst Case Hematology Results Relative to Normal Range Post-Baseline Relative to Baseline	ICH E3	SAC

CONFIDENTIAL

207660

Safety: Tables					
No.	Population	IDSL / Example Shell	Title	Programming Notes	Deliverable
Laboratory: Urinalysis					
3.127.	Safety 1	UR1	Summary of Worst Case Urinalysis Results (Discrete or Character Values) Post-Baseline Relative to Baseline	ICH E3	SAC
Laboratory: Hepatobiliary (Liver)					
3.128.	Safety 1	LIVER1	Summary of Liver Monitoring/Stopping Event Reporting	This display will be presented if liver events occur.	SAC

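### Worst-case laboratory tables set no phase limit, so their by-group percentages depend partly on how many draws each participant's re-treatment timing produces

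*SAP*

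**What the plan says.** References are to the amended plan of 20 August 2018.

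- **Worst-case rule.** Section 8.3 plans worst-case results for chemistry, haematology and urinalysis. It spells out the derivation for urinary protein and occult blood only, by treatment group: "The determination of the worst case post-baseline takes into account both planned and unscheduled assessments". The denominator is equally open: "The percentages are based on the number of subjects in the treatment group with data for the test post-baseline". No phase is named.
- **Tables.** Table 3.44 is titled "Summary of Worst Case Chemistry Results Relative to Normal Range Post-Baseline Relative to Baseline" and Table 3.126 "Summary of Worst Case Hematology Results Relative to Normal Range Post-Baseline Relative to Baseline". These, with 3.48, 3.49, 3.122 and 3.127, use the Safety 1 population and carry only a reference to ICH E3 as programming note. The neighbouring by-visit value and change tables are limited to Screening (values only) and the Blind Phase, plus the Final Visit in the final analysis.
- **Interim data.** Section 3.1 says that all interim analyses "will be performed using data up to Week 24 visit for all participants".
- **Schedule.** Section 10.2.1 plans laboratory tests at screening, at V5 of the blind phase, at V5 of each open-label part and at the Final Visit. None is planned at V1 to V4 or at the retreatment qualification visit (QRV).
- **Unscheduled visits.** Section 10.5.2 keeps them out of summary tables and figures and makes no exception for worst-case results.

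**The concern.** The share of participants with at least one abnormal value rises with the number of values examined. Here that number follows re-treatment, a post-randomisation event linked to response. Section 7.2.3 says that participants still not re-treated after Week 12 are those with lower MAS scores. Section 7.3.7 treats time to qualification for retreatment as an endpoint to be displayed by arm. Each scheduled draw that re-treatment adds also follows an open-label injection of 400 units, given in both groups, so it carries little information on the randomised contrast.

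The plan guards against this elsewhere. Adverse events are tabulated until the second dose, within 84 days and per cycle (Sections 8.1 and 10.4.2). Efficacy summaries stop at Week 12 of each cycle. Section 8.4 excludes open-label data from the ECG and vital-sign summaries. The laboratory worst case has no such window, and the interim set supports a regulatory submission.

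**Working it through.** The plan gives no figure on this point, so there is none to reproduce.

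**Step 1: planned draws at final.** Inputs from Sections 2.3 and 10.2.1:

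- V5 is 12 weeks after each injection.
- "If the participant does not meet the eligibility, QRV will be performed 4 weeks later, at V5 as a starting point"
- No qualification takes place after Week 36.
- "The product can be injected up to 3 times after completion of Part 1 in the blind phase"
- The Final Visit is at Week 48, and a V5 falling at Week 48 is the same visit.

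For participants who complete on nominal weeks there are 1 + 7 + 10 + 1 = 19 possible paths.

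| Injections received | Last injection | Planned post-baseline draws |
|---|---|---|
| 1 | Week 0 | 2 |
| 2 | Weeks 12 to 32 | 3 |
| 2 | Week 36 | 2 |
| 3 | Weeks 24 to 32 | 4 |
| 3 | Week 36 | 3 |
| 4 | Week 36 | 4 |

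Timing matters as well as number: three and four injections can both give 4 draws.

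**Step 2: planned draws at interim.** Under the Section 3.1 cut-offs, a participant re-treated at Week 12 or 16 is followed to the Week 12 visit of the open-label part and has 2 draws. One re-treated at Week 20 is followed only to open-label Week 4 and has 1. One who reaches the Week 24 visit in the Blind Phase also has 1.

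**Step 3: effect of the number of draws.** Assume a chance p of abnormality per draw, the same in both arms, with independent draws. The worst-case rate over k draws is 1 − (1 − p)^k.

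| p (assumed) | k = 1 | k = 2 | k = 3 | k = 4 |
|---|---|---|---|---|
| 2% | 2.0% | 4.0% | 5.9% | 7.8% |
| 5% | 5.0% | 9.8% | 14.3% | 18.5% |
| 10% | 10.0% | 19.0% | 27.1% | 34.4% |

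With perfectly correlated draws the rate stays at p for every k. Positive correlation therefore puts the true figure between the k = 1 column and the value shown.

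**Step 4: gap between arms from draw count alone.**

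- *Interim.* Assume 80% versus 60% re-treated by Week 16. Gap = 0.20 × (rate at k = 2 − rate at k = 1). At p = 5% this is 0.20 × (9.75 − 5.0) = 0.95 points; at p = 10%, 0.20 × (19.0 − 10.0) = 1.8 points. With 60 per group these are about 0.6 and 1.1 participants.
- *Final.* Assume 10/20/70% versus 40/20/40% of participants with 2/3/4 draws. Gap = 0.30 × (rate at k = 4 − rate at k = 2), which is 1.1, 2.6 and 4.6 points at p = 2, 5 and 10%.
- *Final, outer bound.* If one arm had 4 draws throughout and the other 2, the gap would be 3.8, 8.8 and 15.4 points.

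**Step 5: with a blind-phase window.** Each participant reaching blind-phase V5 has one planned draw, so the expected rate is p in both arms and the gap due to planned draw count is 0.

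**The case against.** The strongest counter-case has four parts.

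1. **The explicit rule covers urinalysis only.** This stands. Its result categories do not fit chemistry or haematology, whose tables follow a sponsor shell not reproduced in the plan. Section 8.3 also opens by limiting laboratory summaries to Screening, the Blind Phase and the Final Visit. If that scope governed the worst case, planned draws for completers would be equal: 1 at interim and 2 at final. But that sentence concerns by-visit summaries, and the plan does not extend it to the worst case. For these four tables the supportable statement is that the window is unspecified.
2. **No arm imbalance is shown.** This also stands. Both arms receive the same 240 units in finger and wrist, the plan gives no re-treatment rates by arm, and the detailed re-treatment conditions are not set out in it. A reader might infer that the tables will make one arm look worse; the document does not support that.
3. **Fixed-time displays exist.** True for chemistry and haematology, which have by-visit values, changes and shifts, and Week 12 scatter plots. Urinalysis has only the worst-case summary. A reader might also take these to be the only tables of extremes, but the hepatobiliary abnormality tables (3.51, 3.129) may serve a similar purpose.
4. **The displays are descriptive, and whole-study tables by group are a normal convention.** Accepted: no hypothesis is tested, and the adverse events also have whole-study tables by group. The difference is that adverse events have blind-phase tables beside them.

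**Conclusion.** The point holds as a weakness in specification and method. The worst-case tables have no phase limit, and planned draws vary from 1 to 2 at interim and from 2 to 4 at final with re-treatment timing. By-group percentages can therefore differ without any laboratory effect if that timing differs by arm. It is firm for urinalysis (3.49, 3.127), where the text takes every post-baseline value. For chemistry and haematology (3.44, 3.48, 3.122, 3.126) it rests on the titles and the absence of a limit.

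The likely size is modest: about 1 point at interim under the assumed re-treatment split and 5% per draw. Larger gaps at final need larger differences in re-treatment. All sizes assume a common per-draw risk, independent draws and completers on nominal visits. The documents do not support reading this as a demonstrated bias, or as a reason to drop the whole-study display by group.

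**What to change.** - **Window.** In Section 8.3 and the notes to the six tables, base the between-group worst case on post-baseline values before the second injection and no later than blind-phase V5, in line with the adverse-event windows. For participants re-treated at Week 12, V5 and the second injection normally fall on the same day. Select the V5 draw by visit label, and apply dates to unscheduled draws.
- **Whole-study display.** If wanted, keep it as a separate table labelled descriptive: either pooled (240 + 400U), or by group with the number of draws per participant.
- **Unscheduled values.** In the same edit, reconcile Section 8.3, which counts them, with Section 10.5.2, which excludes unscheduled visits from summary tables. State the rule for chemistry and haematology as well as urinalysis.

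Cost: a few sentences in Section 8.3, six programming notes and a data filter. The downside is one extra set of tables, or open-label extremes moved out of the comparative table.

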#### **8.4. Other Safety Analyses**

The analyses of non-laboratory safety test results including ECGs and vital signs will be based on GSK Core Data Standards, unless otherwise specified. The details of the planned displays are presented in [Appendix 12](#): List of Data Displays.

These above data at Screening Visit, in Blind Phase and at Final Visit will be summarized by visit. These analyses will not include the data at QRV, in Open Label Phase and at Early Withdrawal, whereas all the data at all visit will be listed for final analyses.

ECG findings (Normal, Abnormal – not clinically significant, Abnormal -clinically significant) will be summarized by visit.

Values and changes from baseline in ECG and vital sign data will be summarized by visit.

Values and changes from baseline in SpO2 will be summarized and listed by visit. Data at Screening visit, Visit 1 and 5 in Blind Phase and Final Visit will be summarized and those at all visits will be listed including values and changes from baseline.

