### 2.2. Study Objective(s) and Endpoint(s)

Objectives	Endpoints
Primary Objectives	Primary Endpoints

 
To evaluate the efficacy of the injections of 400 units of the product at Week 6 (finger/ wrist flexors: 240 units, elbow flexors: 160 units), comparing to that of 240 units (finger/ wrist flexors: 240 units, elbow flexors: placebo).
 
	
 
The responder rate: The rate of the participants that Modified Ashworth Scale (MAS) score was reduced at least 1 from baseline in the elbow flexors.
 

Secondary Objectives	Secondary Endpoints

 
To evaluate the efficacy of 400 units of the product, comparing to 240 units of the product
 
	
 
The responder rate of MAS score from baseline in the finger, thumb and wrist flexors
 
Changes in MAS score from baseline in the finger, thumb, wrist and elbow flexors
 
Changes in Disability Assessment Scale (DAS) from baseline
 

	
 
Adverse events
 
Physical examinations
 
Clinical laboratory tests (haematology, blood biochemistry, urinalysis)
 

 
To evaluate the safety and tolerability of the product of 400 units, comparing to 240 units of the product/ To evaluate the safety
 
	

Objectives	Endpoints
and tolerability of 400 units of the product	
 
Vital signs (heart rate, blood pressure, body temperature)
 

Exploratory Objectives	Exploratory Endpoints

 
To evaluate the efficacy of 400 units of the product
 
	
 
Changes in MAS score from baseline in finger, thumb, wrist, elbow, pronation of the forearm and shoulder flexors
 

 
To evaluate the other efficacy of the product of 400 units, comparing to 240 units of the product/ To evaluate the other efficacy of 400 units of the product
 
	
 
Changes in Numeric Rating Scale (NRS) for pain from baseline
 

	
 
Changes in other items of DAS from baseline
 

	
 
Clinical Global Impression of Change (CGI) of functional disability by an investigator
 

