**10.2. Appendix 2: Schedule of Activities**

**10.2.1. Protocol Defined Schedule of Events**

	Screening a	Blind phase 1) If a participant meets the eligibility at V5/ QRV, the participant will move forward to the open- label phase						Open-label phase If a participant meets the eligibility at V5/QRV, the participant will move forward to the next treatment phase						Completion visit
		Part 1					Eligibility evaluation b	Part 2/Part 3/ Part 4				Eligibility evaluation b		
Visit	SV	V1 (Day 1)	V2	V3	V4	V5 c (Eligibility evaluation)	QRV	V1	V2	V3	V4	V5 d (Eligibility evaluation)	QRV	Final Visit
Time from initial injection (Day 1) (Weeks)	—	0	2	4	6	12	Allowable Week 16 to 36 e	—	—	—	—	—	Allowable Week 24 to 36 e	48/ Withdrawal
Time from injection day in each treatment phase (Weeks)	—	0	2	4	6	12	16/ 20/ 24/ 28/ 32/ 36	0	2	4	6	12	16/ 20/ 24	-
Acceptable visit windows (days)		—	±4	±4	±4	+4 f	±14 g	(+4) v	±4	±4	±4	+4 f	±14 g	±4
Written informed consent	X h													
Randomization		X i												
Injections		X						X						
Evaluation of eligibility						X	X					X	X	
Inclusion/exclusion criteria j	X	X i												
Participant demography	X													
MAS k	X	X i	X	X	X	X	X	X i,t	X	X	X	X	X	X
NRS l		X i	X	X	X	X		X i,t	X	X	X	X		(X) r
DAS		X i	X	X	X	X		X i,t	X	X	X	X		(X) r
CGI by a investigator			X	X	X	X			X	X	X	X		(X) r
CGI by a patient			X	X	X	X			X	X	X	X		(X) r
Time to patient-reported onset of spasticity symptom relief			X						X					
Patient-reported benefit of injection				X	X	X				X	X	X		(X) r
Physical examination	X													

CONFIDENTIAL

207660

	Screening a	Blind phase 1) If a participant meets the eligibility at V5/ QRV, the participant will move forward to the open- label phase					Eligibility evaluation b	Open-label phase If a participant meets the eligibility at V5/QRV, the participant will move forward to the next treatment phase					Completion visit	
		Part 1						Part 2/Part 3/ Part 4						Eligibility evaluation b
Visit	SV	V1 (Day 1)	V2	V3	V4	V5 c (Eligibility evaluation)	QRV	V1	V2	V3	V4	V5 d (Eligibility evaluation)	QRV	Final Visit
(complete version)														

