## CONFIDENTIAL

207660

V5 and neutralizing antibody tests will be performed. If V5 in Parts 2 and 3 is performed at Week 36 or later, after completion of V5, completion visit will be performed at Week 48.

- e. QRV is allowable to perform from initial injection to Week 36. Eligibility evaluation (QRV) will not be performed after Week 36.
- f. V5 must be performed at least 84 days after V1.
- g. The acceptable visit windows will be -14 to +4 days if QRV is performed at Week 36.
- h. Must be performed earlier than any other procedures
- i. Must be performed before injection of the product
- j. For inclusion/exclusion criteria, the items to be observed are different between screening phase and Day 1. For details, refer to Protocol Section 6.1 and Section 6.2.
- k. For MAS evaluation, the items to be evaluated differ depending on the treatment phase. For details, refer to Protocol Section 9.1.1.1.
- l. MAS evaluation will be followed by NRS evaluation. For NRS evaluation, items to be evaluated differ. For details, refer to Protocol Section 9.1.1.2.
- m. Body temperature, heart rate, and blood pressure will be measured as vital signs.
- n. Women of childbearing potential will be only performed. Serum hCG pregnancy test must be performed at screening, and urine hCG pregnancy test after randomization. The tests can be performed beyond the protocol specifications if an investigator considers to be necessary.
- o. For laboratory test items, refer to Protocol Section 12.2. Attachment 2. Fasting is not required for blood collection.
- p. Adverse events and serious adverse events collection period will be from the initial injection day (Day 1) to completion visit (FV).
- q. Neutralizing antibody testing is performed 3 times in each participant. The first test will be performed in screening phase, the second is at V5 in the blind phase, and the third is at completion visit.
- r. A participant who withdraws the study before 12 weeks after last injection will be performed.
- s. Perform if V5 in each treatment phase is at Week 48 after initial injection
- t. Not necessary to perform doubly as V1 assessment if the same assessment is performed at V5 or QRV. If V1 assessment or retreatment cannot be performed on the same day as V5 or QRV, MAS assessment should be performed again on the day of visit for the V1 assessment.

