**CONFIDENTIAL**

207660

Unscheduled Visits	

 
• Unscheduled visits will not be included in summary tables and/or figures.
 
• All unscheduled visits will be included in listings.
 
	
Descriptive Summary Statistics	
Continuous Data	Refer to IDSL Statistical Principle 6.06.1 For continuous efficacy endpoints, 95%Confidence Interval will be calculated based on t-distribution.
Categorical Data	N, n, frequency, %
Time to event data	
 
• The number of events and censored case.
 
• 25th and 75th percentiles survival time.
 
• Median survival time with the associated 95% CIs.
 
 95%CIs will be calculated based on Brookmeyer and Crowley method using log-log function as a g-transformation. (This method can be performed using Proc LIFETEST with no special statement or option (SAS 9.4))
Graphical Displays	

 
• Refer to IDSL Statistical Principals 7.01 to 7.13.
 
	

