**10.7. Appendix 7: Reporting Standards for Missing Data****10.7.1. Premature Withdrawals**

Element	Reporting Detail
General	
 
• Participant study completion (i.e. as specified in the protocol) was defined as those who completed all the study procedures, including a completion visit. .
 
• Withdrawn participants were not replaced in the study.
 
• All available data from participants who were withdrawn from the study will be listed and all available planned data will be included in summary tables and figures, unless otherwise specified.
 
• Withdrawal visits will be slotted as per Appendix 3: Assessment Windows or will be summarised as withdrawal visits.
 

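### Vital signs taken at early withdrawal are left out of the summary tables, although for anyone leaving before V5 they are the only scheduled post-dose values

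*SAP*

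**What the plan says.** All references are to the amended SAP.

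- **Endpoint.** Section 2.2 names "Vital signs (heart rate, blood pressure, body temperature") as a secondary safety endpoint.
- **Summaries.** Section 8.4 summarises ECG and vital signs by visit at screening, in the blind phase and at the Final Visit. It adds: "These analyses will not include the data at QRV, in Open Label Phase and at Early Withdrawal". Values from every visit are promised in a listing instead, but only for the final analysis.
- **Schedule (10.2.1).** The vital-sign row has entries at screening, V1 (before injection, footnote i), V5, open-label V1 and V5, and the last column. V2, V3, V4 and QRV are blank. The timing of the last column is "48/ Withdrawal". Footnote f says "V5 must be performed at least 84 days after V1".
- **Unscheduled data (10.5.2).** "Unscheduled visits will not be included in summary tables and/or figures".
- **Withdrawn participants (10.7.1).** For these participants, "all available planned data will be included in summary tables and figures, unless otherwise specified". The next bullet says that withdrawal visits are slotted under Appendix 3 "or will be summarised as withdrawal visits".
- **Displays (10.12).** The vital-sign tables are 3.55-3.56 (interim) and 3.133-3.134 (final). The only vital-sign listing is Listing 67, a final deliverable.

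**The concern.** A by-visit vital-sign table normally loses little when withdrawal visits are left out, because participants contribute earlier post-dose visits. Here there are none: Weeks 2, 4 and 6 have no scheduled vital signs. For someone who leaves before V5, the excluded visit is the whole of the scheduled post-dose record. The rule thus removes a named safety endpoint from the tables for the participants who left early, the group whose safety data a reader would particularly want to see.

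Two further things add to this. Section 10.7.1 gives a general instruction on withdrawal visits that 8.4 does not follow, and neither section refers to the other. And the interim, which section 3.1 says is performed for regulatory submission, has no vital-sign listing to fall back on.

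**Working it through.** The plan states no figure to reproduce. The check is a reading of the schedule, a count of displays and a comparison of two rules.

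**1. Scheduled post-dose vital signs for a participant leaving before V5 (10.2.1)**

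| Visit | Scheduled post-dose sets |
|---|---|
| V1 | 0 (taken before injection) |
| V2, V3, V4 | 0 + 0 + 0 |
| V5 (day 84 or later) | 0 (not reached) |
| Withdrawal | 1 |
| Total | 1 |

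That one set may not be obtained after death or loss to follow-up.

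**2. How many are tabulated.** Section 8.4 excludes the withdrawal set and 10.5.2 excludes anything unscheduled, so 0 of 1 enters the four tables (3.55, 3.56, 3.133, 3.134). The withdrawal record cannot come in as a Final Visit, because 8.4 names Final Visit as summarised and Early Withdrawal as excluded. No other table catches it. Section 8.3 plans worst-case post-baseline displays for laboratory data, but vital signs have only by-visit tables, and Appendix 8 on values of potential clinical importance is marked not applicable.

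**3. How many are listed**

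| Analysis | Listings | Showing vital signs |
|---|---|---|
| Interim | 1-34 (34 listings) | 0 |
| Final | 35-68 (34 listings) | 1 (Listing 67) |

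The interim gap is a separate matter from the withdrawal clause: it affects every participant. Others at least have V5 values in Tables 3.55-3.56. Early leavers have no post-dose value in any interim vital-sign display.

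**4. Section 8.4 against 10.7.1.** The bullet on planned data allows exceptions specified elsewhere, and 8.4 can be such an exception. The bullet on withdrawal visits carries no such wording and offers two routes. The first, Appendix 3, covers efficacy only, and its listed cases except withdrawn participants, so it cannot slot a vital-sign visit. That leaves the second, summarising as a withdrawal visit, which 8.4 rules out.

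**5. Size.** Each affected participant is 1/60 = 1.7% of an arm. The SAP gives no withdrawal rate. As an assumption only, if 2% to 10% left before Week 12, that would be 0.02 × 60 = 1.2 to 0.10 × 60 = 6, or about 1 to 6 participants per arm.

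**6. Scope.** The point is confined to vital signs. ECG has no entry in the withdrawal column, so excluding early withdrawal costs no scheduled ECG.

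**The case against.** The exclusion looks deliberate. The April 2018 plan (its section 7.4) had no such sentence; the amended plan adds it, pairs it with full listing at the final analysis, and has table notes that agree with it. A by-visit table at fixed times is a defensible display, and withdrawal values taken at arbitrary times do not belong in a V5 mean. The same sentence also leaves out open-label data for everyone. All of this stands, and it is why any added row should be separate and the existing rows left alone.

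A reader might infer that 8.4 and 10.7.1 flatly contradict each other. The documents do not go that far. Section 10.7.1 is a general reporting standard and its preceding bullet defers to exceptions. Its withdrawal-visit bullet can be read as saying how such a visit is labelled when it is summarised. A programmer would probably follow the rule that names these data. What remains is an untidiness: that bullet has no exception of its own, and nothing says that 8.4 overrides it.

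A reader might also infer that safety in early leavers is hidden. It is not. Treatment-emergent adverse events are counted up to the early-withdrawal date (10.4.2), and adverse events leading to withdrawal have tables by arm at both analyses (3.37-3.39 and 3.113-3.115). The vital-sign values themselves are listed at the final analysis.

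Finally, a pooled row for a handful of people at mixed times tells a reader little beyond the individual values. That limits the gain. It does not explain why a scheduled safety measurement should be in no table, and in no interim display at all.

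**Conclusion.** The point holds and is minor. For a participant who leaves before V5, 0 of 1 scheduled post-dose vital-sign sets is tabulated. The set is listed once, at the final analysis, and is not shown at the interim. This follows from the schedule, 8.4 and 10.5.2 alone and does not depend on how the overlap with 10.7.1 is resolved. The number affected is unknown; disposition Table 1.01 will show withdrawals by Week 24.

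It would be too strong to say that the omission biases the trial's safety conclusions. No efficacy or adverse-event result changes, the summaries are descriptive, and nothing in the SAP indicates how many participants would be involved or in which arm.

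**What to change.** 1. In 8.4, state that vital signs at early withdrawal before the second dose are shown by arm in one separate withdrawal row of Tables 3.55-3.56 and 3.133-3.134. Leave the by-visit rows, including V5, unchanged. The limit to the period before the second dose keeps the comparison between arms meaningful, because both groups receive 400 units afterwards.
2. Make the vital-sign listing (now Listing 67, final only) an interim deliverable as well.
3. In 10.7.1, add that vital signs at open-label withdrawal are listed only, as an exception under 8.4. Without this, a row limited to the blind phase would leave the two sections only partly aligned.

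The cost is small: a wording change in two sections, one row in four tables and one existing listing run twice, all from data already scheduled for collection. The downside is a sparse row whose values fall at mixed times, which a footnote should say.
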